2. AIMS/OBJECTIVES

2.1 Primary Aim is to determine if control of nausea at Cycle 2 in participants who experienced CINV at Cycle 1 is improved by the addition of either prochlorperazine or olanzapine to the control arm of netupitant, palonosetron and dexamethasone.

2.1.1 Hypothesis 1: Control of nausea at Cycle 2 in participants who experienced CINV at Cycle 1 despite receiving an ASCO-recommended antiemetics(1) can be improved by the addition of either prochlorperazine or olanzapine to the standard antiemetic combination of netupitant, palonosetron and dexamethasone.

2.2 Secondary Aim 1 is to determine if olanzapine is more effective than prochlorperazine in controlling nausea at Cycle 2 in participants who experienced CINV at Cycle 1 when used in combination with netupitant, palonosetron and dexamethasone.

2.2.1 Hypothesis 2: Olanzapine, which is a newer antiemetic drug with a more problematic side-effect profile than prochlorperazine, is more effective than prochlorperazine in controlling nausea when used in combination with netupitant, palonosetron and dexamethasone.

2.3 Secondary Aim 2 is to determine if control of vomiting at Cycle 2 in participants who experienced CINV at Cycle 1 is improved by the addition of either prochlorperazine or olanzapine to the control arm of netupitant, palonosetron and dexamethasone.

2.3.1 Hypothesis 3: Control of **vomiting** at Cycle 2 in participants who experienced CINV at Cycle 1 despite receiving an ASCO-recommended antiemetic regimen(1) can be improved by the addition of either prochlorperazine or olanzapine to the standard antiemetic combination of netupitant, palonosetron and dexamethasone.

2.4 Secondary Aim 3 is to determine if olanzapine is more effective than prochlorperazine in controlling vomiting at Cycle 2 in participants who experienced CINV at Cycle 1 when used in combination with netupitant, palonosetron and dexamethasone.

2.4.1 Hypothesis 4: Olanzapine, which is a newer antiemetic drug with a more problematic side-effect profile than prochlorperazine, is more effective than prochlorperazine in controlling **vomiting** when used in combination with netupitant, palonosetron and dexamethasone.

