7.2 Secondary Endpoints

The outcome variable for secondary aim 1 will be average nausea as described above. The outcome variable for secondary aims 2 and 3 will be Any Vomiting (yes/no).

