14.2 Data Handling

Data will be analyzed as intent-to-treat. The assumptions underlying all statistical analyses will be thoroughly checked using appropriate graphical and numerical methods.(42,43) In the case of serious violations of the assumptions, appropriate nonparametric methods or transformations will be attempted.(44,45) In the event of outlying observations, we will carefully check the data and make corrections if necessary. If no errors are found, we will conduct analyses both with and without the outlying data and report both results to assess the sensitivity. All hypothesis testing will be performed at the two-sided 0.05 level, with the exception of the Primary Analysis, which will use the 0.05/2=0.025 level. SAS, JMP and R will be used for the analyses as appropriate.

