14.5 Primary Objectives and Analysis Plans

14.5.1 The **Primary Aim** is to determine if control of nausea at Cycle 2 in participants who experienced CINV at Cycle 1 is improved by the addition of either prochlorperazine or olanzapine to the control arm of netupitant, palonosetron and dexamethasone.

14.5.2 **Primary Hypothesis:** Control of nausea at Cycle 2 in participants who experienced CINV at Cycle 1 despite receiving ASCO-recommended antiemetics(1) can be improved by the addition of either prochlorperazine or olanzapine to the standard antiemetic combination of netupitant, palonosetron and dexamethasone.

14.5.3 **Primary Analysis:** We will use a one-way analysis of variance on Post – Pre change scores. We have Arms 1 (control), 2, and 3. Two tests will be done using contrasts: 1 vs. 2 and 1 vs. 3, using a significance level of $0.05 / 2 = 0.025$.

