14.6 Secondary Objectives, Endpoints, Analysis Plans

14.6.1 **Secondary Aim 1** is to determine if olanzapine is more effective than prochlorperazine in controlling nausea at Cycle 2 in participants who experienced CINV at Cycle 1 when used in combination with netupitant, palonosetron and dexamethasone. This will be assessed by estimating the contrast $D = (3 - 1) - (2 - 1)$, where 3 is the Arm 3 mean, 2 is the Arm 2 mean, and 1 is the Control mean, and testing whether $D = 0$ versus the one-sided alternative hypothesis that $D > 0$.

14.6.2 **Secondary Aims 2 and 3** will compare the effects of the interventions on vomiting

by fitting a generalized linear model. The response will be Any Vomiting (yes/no) after Cycle 2, treatment arm as the main factor, and Any Vomiting after Cycle 1 as a covariate. Estimation will be performed using maximum likelihood assuming a binomial distribution and logit link. The same group of contrasts described in the Primary Aim analysis will be estimated and tested, with a significance level of 0.025 to adjust for multiple tests.

14.7 Exploratory Analyses:

14.7.1 We will create an empirically-based algorithm predicting nausea from breast cancer chemotherapy regimens. To do so, we will use the Cycle 1 diary data (total N = approximately 1600 overall) to develop a predictive model for the risk of developing nausea, using age, race, ethnicity, QOL, alcohol consumption, susceptibility to nausea, expectancy, anxiety, level of nausea on the day prior to treatment, and prior history of nausea as potential predictors. For this analysis, the outcome will be binary, with Nausea=YES if Peak Nausea ≥ 3 and NO otherwise. We will apply two modeling paradigms: 1) Classification Trees, and 2) logistic regression.

14.7.1.1 Classification trees consist of finding a series of binary rules with which to base classifications, e.g., if Age is under 65, Race is Caucasian, and highly emetogenic chemotherapy agents are used, there is a X% risk of CINV. These models are very easy to apply in practice and have been shown to be especially effective if there are interactions between the predictors in the model.(47) We will use Conditional Tree methodology for the computations.(48)

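### Section 14.6.2 plans no olanzapine-versus-prochlorperazine contrast for vomiting (Secondary Aim 3), and the levels and direction of the secondary tests need reconciling with section 14.2 and Hypothesis 2

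*Combined protocol and SAP*

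**What the plan says.** **Vomiting.** Section 2.4 states that "Secondary Aim 3 is to determine if olanzapine is more effective than prochlorperazine in controlling vomiting at Cycle 2", and 2.4.1 turns this into Hypothesis 4. Section 7.2 gives the endpoint: "The outcome variable for secondary aims 2 and 3 will be Any Vomiting (yes/no"). Section 14.6.2 covers both aims with a binomial model with logit link, treatment arm as the factor and Cycle 1 vomiting as covariate. Its testing sentence is "The same group of contrasts described in the Primary Aim analysis will be estimated and tested, with a significance level of 0.025". The contrasts it refers to are set in 14.5.3: "Two tests will be done using contrasts: 1 vs. 2 and 1 vs. 3".

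**Level.** Section 14.2 reads "All hypothesis testing will be performed at the two-sided 0.05 level, with the exception of the Primary Analysis", which uses 0.025. Section 14.6.2 tests the vomiting contrasts "with a significance level of 0.025 to adjust for multiple tests".

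**Nausea, Secondary Aim 1.** Section 7.2 says "The outcome variable for secondary aim 1 will be average nausea as described above". Section 14.6.1 defines D = (3 - 1) - (2 - 1) in terms of arm means and tests D = 0 "versus the one-sided alternative hypothesis that" D > 0. It states no level.

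**The concern.** Secondary Aim 3 compares Arm 3 with Arm 2. Each contrast listed in 14.5.3 compares an active arm with control. If 14.6.2 is followed exactly, Hypothesis 4 is not tested, and its contrast, sidedness and level would have to be chosen outside the plan, possibly after unblinding.

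On the level, a vomiting p-value between 0.025 and 0.05 is significant under 14.2 and not under 14.6.2.

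On Secondary Aim 1, the one-sided form conflicts with 14.2, and the written direction seems opposite to Hypothesis 2, which says olanzapine controls nausea better. Between them, these points touch both of the plan's olanzapine-versus-prochlorperazine aims.

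**Working it through.** **1. Which contrasts are planned for vomiting.** With arms ordered (1, 2, 3):

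- 2 vs. 1 is (-1, +1, 0) and 3 vs. 1 is (-1, 0, +1). These are the two contrasts of 14.5.3.
- Aim 3 needs 3 vs. 2, which is (0, -1, +1).
- (3 - 1) - (2 - 1) = (0, -1, +1). The Aim 3 contrast is the difference of the two planned ones, so the same model can estimate it, but testing each planned contrast does not test their difference.

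Section 14.7.2 is a useful comparison. For quality of life it points to the procedures of both the Primary Aim and the first Secondary Aim, which brings in 3 vs. 2. Section 14.6.2 points to the Primary Aim alone.

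**2. Where 0.025 comes from.** It is 0.05/2, a split over two tests. The plan's power figure reproduces at that level. Inputs from 14.3: SD of change 0.953, difference 0.48, 100 evaluable per arm.

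- SE = 0.953 × sqrt(2/100) = 0.1348, and 0.48/0.1348 = 3.56.
- Two-sided 0.025 has critical value 2.241. Power = Φ(3.56 - 2.241) = 0.907 by the normal approximation, or 0.904 by noncentral t with 297 df. The plan states 90%.

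**3. Familywise error for the vomiting tests.** Global null, two-sided tests, equal independent arms, normal approximation for the logistic contrasts. The two contrasts against control correlate 0.5.

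| Tests | Level each | Approximate familywise error |
|---|---|---|
| 2 vs. 1, 3 vs. 1 (14.6.2 as written) | 0.025 | 0.046 |
| 2 vs. 1, 3 vs. 1 (14.2 rule) | 0.05 | 0.091 |
| All three | 0.05/3 = 0.0167 | 0.044 |
| All three | 0.025 | 0.064 |
| Aim 2 pair, and 3 vs. 2 as a separate family | 0.025 for the pair, 0.05 for 3 vs. 2 | 0.085 |

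Once 3 vs. 2 is added, the two-test split no longer holds 0.05 over all three.

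**4. Direction in 14.6.1.**

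- D reduces to the Arm 3 mean minus the Arm 2 mean, that is olanzapine minus prochlorperazine.
- The nausea scale in 14.4 runs from no nausea to extreme nausea, and entry to Cycle 2 requires a score of at least 3 (3.2.1), so higher is worse.
- The only scoring the plan gives is Post minus Pre (14.5.3).
- On that scoring, D > 0 means more nausea, or less reduction, on olanzapine. Hypothesis 2 requires D < 0.

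**5. Illustration of the consequence.** Assumptions: the 0.48 that 14.3 states for active arm against control also applies to olanzapine against prochlorperazine; SD 0.953; 100 per arm; one-sided level 0.05, since 14.6.1 gives none. True D = -0.48, a standardised shift of 3.56.

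- One-sided test of D > 0, as written: P(Z > 1.645 + 3.56) ≈ 1e-7.
- One-sided test of D < 0: Φ(3.56 - 1.645) = 0.972.
- Two-sided 0.05: Φ(3.56 - 1.960) = 0.945.

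**The case against.** **Aim 3 is named, so it is covered.** Section 14.6.2 names Aim 3 and supplies its outcome, model and covariate, so the intent to address it is plain and nothing is lost from the data. That stands. A reader might go further and infer that 3 vs. 2 is implied, or conversely that the trial cannot answer Aim 3. The documents support neither: the contrast is not in the set referred to, and the specified model can estimate it. What is missing is the contrast, its sidedness and a level that takes account of a third test.

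**The 0.025 rule is specific and stricter than 14.2.** This stands. A reader might infer inflated error from the conflict, but following 14.6.2 gives about 0.046. The 0.091 arises only if the explicit sentence in 14.6.2 is set aside. The defect is that 14.2 as worded does not admit the exception.

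**Aim 3 could simply take the 0.05 default.** A reader might infer this from 14.2. But the only adjustment written for vomiting sits under a heading that joins Aims 2 and 3, so the text does not settle whether they form one family. That choice belongs to the sponsor.

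**The arm means in 14.6.1 are not defined.** If they were improvement scores, D > 0 would agree with Hypothesis 2, and symbols may have suffered when the text was extracted. No section defines an improvement score, so apparently reversed is the fair description; a firm claim that the authors meant to test for harm is not supported. One-sidedness is not itself an error either, because Hypothesis 2 is directional. The faults are the unreconciled conflict with 14.2 and the missing level.

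**Conclusion.** The point holds in three parts of unequal weight.

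1. **Core.** Hypothesis 4 has no planned contrast. This rests on the text alone.
2. **Level.** Sections 14.2 and 14.6.2 disagree for the vomiting contrasts. This is a wording conflict with no inflation of error if 14.6.2 is followed.
3. **Aim 1.** The test conflicts with the two-sided rule of 14.2, has no stated level, and on the plan's only stated scoring points away from Hypothesis 2.

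The familywise figures are normal approximations under the global null. The power figures for Aim 1 are illustrations that borrow the 0.48 and assume a one-sided 0.05 level; the plan states no expected difference between the two active arms. It gives no vomiting rates either, so power for Aim 3 cannot be checked. The effect is confined to secondary aims and to the exploratory FACT-G analysis that reuses the Aim 1 procedure. The primary analysis and N = 333 are unaffected. It should be fixed before unblinding.

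**What to change.** - **14.6.2:** keep 1 vs. 2 and 1 vs. 3 for Aim 2. For Aim 3 add 3 vs. 2 from the same logistic model, reported as an odds ratio with confidence interval, with its sidedness and level stated before unblinding. The sponsor chooses the level and discloses the matching familywise error from the table above: all three at 0.0167, all three at 0.025, or Aim 2 at 0.025 with Aim 3 as a separate family at 0.05.
- **14.2:** list the vomiting contrasts, at their chosen level, as an exception to two-sided 0.05.
- **14.6.1:** state that the means are Post minus Pre nausea changes. Then either make the test two-sided at 0.05, or keep it one-sided with alternative D < 0 and a stated level listed as an exception in 14.2.
- **14.7.2:** because it reuses the 14.6.1 procedure, state there the direction that represents benefit on FACT-G.

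The cost is a few sentences. No new data, model or sample size is needed.

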14.8 Interim Analysis

There will be no interim analysis for this protocol.

14.9 Ancillary Studies

Ancillary studies could include secondary data analyses and use of blood samples for future research.

15. ETHICAL AND REGULATORY CONSIDERATIONS

15.1 Institutional Review Board Approval

Prior to initiating the study and receiving agent, the NCORPs must obtain written approval to conduct the study from the NCI Central IRB. Should changes to the study become necessary, protocol amendments will be submitted to the DCP PIO according to DCP Amendment Guidelines. The DCP-approved amended protocol must be approved by the CIRB prior to implementation of any changes.

After the study is closed to accrual, it should not be permanently closed at the community sites until notified to do so by the URCC NCORP Research Base.

15.2 Submission of Regulatory Documents

All regulatory documents are reviewed at the NCORP for completeness and accuracy prior to submission to URCC. Once review is completed by the NCORP, the original regulatory documents are forwarded to the URCC Regulatory Compliance Specialist as follows:

[contact]

15.3 Other

This trial will be conducted in compliance with the protocol, Good Clinical Practice, and the applicable regulatory requirements.

16. FINANCING, EXPENSES, AND/OR INSURANCE

This study is supported by the URCC NCORP Research Base grant UG1CA189961 and R01 CA200579. There are no expenses to the participant for participating in this study and they will not be paid for their participation.

